4. ANALYSIS SETS (POPULATIONS FOR ANALYSIS)

Data for all participants will be assessed to determine if participants meet the criteria for inclusion in each analysis population prior to unblinding and releasing the database, and classifications will be documented per standard operating procedures.

Population	Description
Screened	All participants who sign the ICD.
Randomized	All participants who are assigned a randomization number in the IWRS.
Evaluable immunogenicity (HAI assays CCI [REDACTED])	All participants included in the immunogenicity subset who are eligible, receive the study intervention to which they were randomized, have blood drawn for assay testing within the specified time frame (CCI [REDACTED]), have at least 1 valid and determinate assay result (HAI assays CCI [REDACTED]) at the 4-week postvaccination visit, and have no important protocol deviations.
Evaluable immunogenicity (HAI assays CCI [REDACTED])	All participants included in the immunogenicity subset who are eligible, receive the study intervention to which they were randomized, have blood drawn for assay testing within the specified time frame (CCI [REDACTED]), have at least 1 valid and determinate assay result (HAI assays CCI [REDACTED]) at the 4-week postvaccination visit, and have no important protocol deviations.
mITT immunogenicity (HAI assays CCI [REDACTED])	All randomized participants in the immunogenicity subset who receive the study intervention and have at least 1 valid and determinate assay result (HAI assays CCI [REDACTED]) after vaccination.
mITT immunogenicity (HAI assays CCI [REDACTED])	All randomized participants in the immunogenicity subset who receive the study intervention and have at least 1 valid and determinate assay result (HAI assays CCI [REDACTED]) after vaccination.
Evaluable efficacy	All participants who are eligible, receive the study intervention to which they were randomized, and have no important protocol deviations, with surveillance starting at least 14 days after vaccination.
mITT efficacy	All randomized participants who receive the study intervention.

Population	Description
Safety	All participants who receive the study intervention.
Reactogenicity e-diary safety	All participants who receive the study intervention and have at least 1 day of e-diary data transferred for reactogenicity.

In addition, the mITT analysis set will be defined for participants who consent for isolation of CCI [REDACTED] and also for participants who may be selected for CCI [REDACTED]
[REDACTED].

mITT immunogenicity (CCI [REDACTED])	All randomized participants in the immunogenicity subset who receive the study intervention and have at least 1 valid and determinate CCI [REDACTED] sample result after vaccination.
mITT immunogenicity CCI [REDACTED]	All randomized participants in the immunogenicity subset who receive the study intervention and have at least 1 valid and determinate CCI [REDACTED] result after vaccination.

Important protocol deviations will be determined by clinical review. An important protocol deviation is a protocol deviation that, in the opinion of the sponsor's study medical monitor, would materially affect the assessment of immunogenicity or efficacy, eg, participant receipt of a prohibited vaccine or medication/treatment that might affect immune response or a medication error with suspected decrease in potency of the vaccine. The sponsor's medical monitor will identify those participants with protocol deviations before any analysis is carried out.

Note, participants who have confirmed cases prior to an important protocol deviation are included in the evaluable efficacy population.

The APE field will be included in the PIPD list from the CORD system and is used to help identify protocol deviations that may exclude participants from a particular population. For each reporting event, the most current endorsed version of the PIPD list must be used to generate the protocol deviation data set for analysis and reporting.

The APE flags for this study are as follows:

- YES-POP1 (participants excluded from the safety population)
- YES-POP2 (participants excluded from the evaluable immunogenicity populations CCI [REDACTED])
- YES-POP3 (participants excluded from the evaluable efficacy population)
- YES-POP4 (participants identified as multiple enrollments at different sites)

The safety analyses are based on the safety population. Participants will be summarized by study intervention group according to the study interventions they actually received.

For all the immunogenicity endpoints, the analysis will be based on the appropriate evaluable immunogenicity population. An additional analysis may be performed based on the mITT immunogenicity population if there is a large enough difference ^C in sample size¹ between the mITT immunogenicity population and the evaluable immunogenicity population separately for each assay type. Participants will be summarized according to the study intervention group to which they were randomized.

Vaccinated but not randomized: These participants will be included in the safety population for safety analysis and will be reported under the study intervention based on the vaccine received but will be excluded from immunogenicity analyses and efficacy analysis.

Randomized but not vaccinated: These participants will be included in the randomly assigned population and excluded from any safety analyses.

Randomized but received incorrect vaccine: These participants will be excluded from the evaluable populations for immunogenicity and efficacy analysis but will be included in the mITT populations for immunogenicity and efficacy analyses if data are available and will be reported under the study intervention based on the randomized vaccine. These participants will also be included in the safety population for safety analysis and will be reported under the study intervention based on the vaccine received.

Participants who had important protocol deviations or discontinued from the study before Day 15 (within 2 weeks after vaccination) will be excluded from the evaluable efficacy population.

Participants who were enrolled in the wrong age cohort per their chronological age at the time of enrollment and who were dosed with the study vaccination will be excluded from the evaluable efficacy and evaluable immunogenicity populations. These participants will be included in the mITT population for immunogenicity and efficacy analyses. Safety data for these participants will be populated on listings separate from those participants enrolled in the correct cohort.

Participants who were enrolled in the wrong age cohort per their chronological age at the time of enrollment but were dosed with licensed QIV will not be excluded from the evaluable efficacy and evaluable immunogenicity populations if there are no important protocol deviations and they are meeting other criteria of the evaluable efficacy/immunogenicity population. Safety data for these participants will be included with all participants who received licensed QIV per their chronological age at the time of enrollment.

Participants enrolling at multiple sites: Any participant enrolling at more than 1 site in the study will be removed from the evaluable, mITT, and safety populations. These participants will be followed for safety and reported separately from the other participants.

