#### 9.3.1. General Considerations

CIs for all endpoints in the statistical analysis will be presented as 2-sided at the 95% level unless specified otherwise.

For all the efficacy endpoints, the analyses will be performed on both the evaluable efficacy population and the mITT efficacy population; the main analysis will be based on the evaluable efficacy population. Participants will be summarized according to the vaccine group to which they were randomized for the mITT efficacy population.

The safety analyses are based on the safety population. Participants will be summarized by vaccine group according to the study interventions they actually received. Completely missing reactogenicity e-diary data will not be imputed; missing AE dates will be handled according to the Pfizer safety rules.

For all the immunogenicity endpoints (HAIs CCI [REDACTED]), the analysis will be based on the evaluable immunogenicity populations. Antibody titers below the LLOQ or denoted as BLQ will be set to CCI [REDACTED] for immunogenicity analysis. All immunogenicity analyses will be performed after the imputation of the antibody concentrations or antibody titers that are below the LLOQ.

An additional analysis may be performed based on the mITT immunogenicity populations (HAIs CCI [REDACTED]) if there is a large enough difference in sample size between the mITT immunogenicity population and the evaluable immunogenicity population. Participants will be summarized according to the vaccine group to which they were randomized. Missing serology data will not be imputed.

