 - **Intercurrent events:** All data after an intercurrent event (receiving a prohibited vaccine or concomitant therapy, receiving the vaccine not as randomized, missing e-diary entries on certain days, discontinuation of the study, etc), if collected, will be included.
 - **Population-level summary:** The rates of reporting each prompted reactogenicity item and/or coded reactogenicity AE will be estimated, by study intervention (qIRV or seasonal QIV), for each age group (18 through 64 years of age, ≥ 65 years of age).
- The AE and SAE estimands have the following 5 attributes:
 - **Population:** Participants 18 years of age or older who receive 1 dose of study intervention.
 - **Variables:**
 - AEs reported through 4 weeks after vaccination.
 - SAEs reported through 6 months after vaccination.
 - **Treatment condition:** qIRV, or seasonal QIV, administered on Day 1.
 - **Intercurrent events:** All data after an intercurrent event (receiving a prohibited vaccine or concomitant therapy, receiving the vaccine not as randomized, discontinuation of the study, etc), if collected, will be included.
 - **Population-level summary:** The rates of reporting AEs and SAEs will be estimated, by study intervention (qIRV or seasonal QIV), for each age group (18 through 64 years of age, ≥ 65 years of age) and overall (≥ 18 years of age).

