6.1.3. AEs and SAEs

6.1.3.1. Main Analysis

- Estimand strategy: Treatment policy ([Section 2.2.1](#)).
- Analysis set: Safety population ([Section 4](#)).
- Analysis methodology: 95% CI of the proportion of participants reporting those events, using the Clopper-Pearson method ([Section 5.2.1](#)).
- Analysis timing: Day 1 through 4 weeks after vaccination for AEs; Day 1 through 6 months after vaccination for SAEs.
- Intercurrent events and missing data: All data collected are included. Missing AE dates will be imputed as described in Pfizer's Vaccine Statistics Rulebook.
- Reporting results:
 - The number of participants with AEs through 4 weeks after vaccination (n), proportion (%), and associated 2-sided Clopper-Pearson 95% CI, will be presented by each study intervention group, separately, for each analysis interval ([Section 3.1.2.4](#)), and for each age group (18 through 64 years of age, ≥ 65 years of age), and overall.
 - The number of participants with SAEs through 6 months after vaccination (n), proportion (%), and associated 2-sided Clopper-Pearson 95% CI will be presented by each study intervention group, separately, for each analysis interval ([Section 3.1.2.5](#)), and for each age group (18 through 64 years of age, ≥ 65 years of age), and overall.
 - Descriptive statistics, including the proportion (%), the numerator (n) and the denominator used in the proportion calculation, and the 95% CI for percentage using the Clopper-Pearson method, will be presented, by each SOC and PT within each SOC, by study intervention group for each age group (18 through 64 years of age, ≥ 65 years of age), and overall.

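### SAP Section 4 treats the safety data of wrong-age-cohort participants differently by arm, and on its natural reading leaves some vaccinated qIRV recipients out of the primary AE and SAE tables

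*SAP*

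**What the plan says.** SAP Section 4 (Analysis Sets) has two consecutive paragraphs on participants enrolled in the wrong age cohort.

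- **Given the study vaccination.** Such participants, "per their chronological age at the time of enrollment and who were dosed with the study vaccination will be excluded from the evaluable efficacy" population and from the evaluable immunogenicity populations; they stay in the mITT sets. On safety: "Safety data for these participants will be populated on listings separate from those participants enrolled in the correct cohort".
- **Given licensed QIV.** They stay in the evaluable sets if otherwise qualified. On safety: "Safety data for these participants will be included with all participants who received licensed QIV per their chronological age at the time of enrollment".

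The rest of the plan describes an all-vaccinated safety analysis.

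- The safety population in SAP Section 4 is "All participants who receive the study intervention". Protocol 9.2 has the same definition. Neither has an age-cohort condition.
- Protocol 9.3.1: "Participants will be summarized by vaccine group according to the study interventions they actually received". SAP Section 4 repeats this.
- SAP 2.2.1 applies a treatment policy strategy to AEs and SAEs. Data after intercurrent events such as "receiving the vaccine not as randomized, discontinuation of the study, etc), if collected, will be included".
- SAP 6.1.3.1, the main AE and SAE analysis, has "Analysis set: Safety population" and "Intercurrent events and missing data: All data collected are included". It reports each age group and overall.

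**The concern.** The primary safety objective is to define the safety profile of qIRV. A programmer who follows the wrong-cohort paragraph would take these qIRV recipients, and any events they had, out of both numerator and denominator, while leaving QIV recipients with the same error in place. A programmer who follows the population definition and SAP 6.1.3.1 would keep everyone. The two would produce different primary safety tables from the same data.

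Under the first reading, the between-group AE differences in SAP 6.6.1 and the combined rates for all adults would rest on sets chosen by a rule that depends on the vaccine received. For common events this would hardly show. For a rare event, such as the one AESI (confirmed myocarditis or pericarditis), a single case shown in a listing and not in a table changes the tabulated rate visibly.

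**Working it through.** **1. To whom the listing rule applies.** The first paragraph speaks of the study vaccination and the second deals separately with licensed QIV. If the first covered both vaccines, the two would contradict each other for QIV recipients. So the first paragraph means qIRV.

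**2. How Section 4 and its neighbors word inclusion and removal.**

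| Group | Place | Treatment of safety data |
|---|---|---|
| Vaccinated, not randomized | SAP 4 | Expressly kept in the safety population |
| Received the wrong vaccine | SAP 4 | Expressly kept, under vaccine received |
| Randomized, not vaccinated | SAP 4 | Expressly left out of safety analyses |
| Enrolled at several sites | SAP 4 | Expressly removed from the safety population |
| Events before vaccination | SAP 6.1.3.2 | Expressly listed and not analyzed |
| Wrong cohort, QIV | SAP 4 | Expressly pooled with other QIV recipients |
| Wrong cohort, qIRV | SAP 4 | Separate listings; silent on population and tables |

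Only the last row leaves the question open. Its contrast with the QIV row points to omission from the tables: a listing that merely added to the tables would need no different QIV rule. The absence of any removal wording points the other way. Section 4 also has a flag (YES-POP1) for exclusion from the safety population and does not say what sets it.

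**3. The plan's own safety figure.** Protocol Table 7 gives the probability of seeing at least one event, 1 − (1 − p)^N. With p = 0.01% and N = 18,100 this is 0.8364, matching the stated 0.84. With N = 8,800 and 9,300 it is 0.5852 and 0.6055, matching 0.59 and 0.61. Dropping 100 people from 18,100 gives 0.8347, so Table 7 is not at issue.

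**4. Size of the effect.** Inputs:
- N = 36,200 / 2 = 18,100 qIRV recipients. The 36,200 is initial enrollment in SAP 2.3. The allocation ratio is redacted, so 1:1 is assumed; 18,100 is a Table 7 column.
- k, the number of wrong-cohort qIRV recipients, is not in the documents. Assumed 1 to 100.
- Event rate r_c in correctly enrolled participants: assumed 1% or 10%. Rate r_w in the wrong-cohort group: assumed 1, 2 or 5 times r_c, or 100% for the bound.

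Rate with everyone included minus rate with the k dropped = k × (r_w − r_c) / N. If r_w = r_c, the shift is zero.

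| N | k | r_w | Shift, r_c = 1% | Shift, r_c = 10% |
|---|---|---|---|---|
| 18,100 | 1 | all have the event | 0.005 points | 0.005 points |
| 18,100 | 10 | 2 × r_c | 0.0006 | 0.0055 |
| 18,100 | 10 | all have the event | 0.055 | 0.050 |
| 18,100 | 100 | 5 × r_c | 0.022 | 0.221 |
| 18,100 | 100 | all have the event | 0.547 | 0.497 |
| 8,800 (one stratum) | 100 | 5 × r_c | 0.046 | 0.455 |
| 8,800 (one stratum) | 100 | all have the event | 1.125 | 1.023 |

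Shifts are in percentage points. For example, 100 × (1 − 0.01) / 18,100 = 0.547%.

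**5. Rare events, as a hypothetical.** Suppose two AESI cases in the qIRV arm, one of them in a wrong-cohort participant. With that one participant left out, the tabulated rate goes from 2 / 18,100 = 11.0 to 1 / 18,099 = 5.5 per 100,000. This is unlikely under equal risk: if 9 to 90 of 18,100 were wrong-cohort, the chance that at least one of two cases falls among them is 1 − (1 − 9/18,100)² = 0.1% to 1 − (1 − 90/18,100)² = 1.0%.

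**The case against.** A reader might infer that the primary AE and SAE rates definitely drop vaccinated people from the qIRV arm and that their data appear on listings *only*. The documents do not support that. The word *only* is absent. The paragraph names exclusion from the evaluable efficacy and immunogenicity sets and no other exclusion. Where the SAP means removal or listing without analysis, it says so outright, as for multi-site enrollees and prevaccination events. These participants meet the definition of the safety population, and SAP 6.1.3.1 analyzes that population. The listing could therefore be an addition to the tables. This objection stands against certainty. It leaves two readings that give different primary tables.

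There is also a plausible reason for treating the arms differently. SAP 2.3 says the qIRV dose level may differ by age stratum, and protocol 4.1 sets it by stratum with the values redacted. If the levels differ, a wrong-cohort qIRV recipient may have received the other stratum's level, and a separate display keeps each stratum's table tied to one level. That could justify separation within a stratum. It does not by itself explain omission from the overall analysis of all adults, and the SAP does not offer it as a reason.

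Finally, no case would be hidden. An AESI is still recorded, reported and listed, and the external committee monitors safety throughout. That protects participants and limits the harm, but it does not settle which people the primary tables count.

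**Conclusion.** The point holds as an unresolved conflict with an asymmetry between arms. The asymmetry is in the text. Omission from the qIRV tables is the most natural reading of the listing sentence, but it remains an inference. On that reading the rule contradicts the safety population, the treatment policy estimand and the main AE and SAE analysis.

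The effect on common AE rates is probably negligible. Over the assumed range of 1 to 100 affected qIRV recipients out of 18,100, the largest possible shift runs from about 0.005 to 0.55 percentage points, and the upper end requires all 100 to have the event. These figures rest on 1:1 allocation and on an assumed count, since the documents give neither. The AESI example shows how a tabulated rate would respond; it is not a forecast. The case for a change rests on a primary-objective analysis having contradictory, arm-dependent instructions that are cheap to settle. It should be settled before analysis.

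**What to change.** In SAP Section 4, state that all vaccinated participants, except the multi-site enrollees already specified, count in the numerator and denominator of the AE and SAE tables by vaccine actually received, at minimum in the overall analysis of participants 18 years and older. Make the wrong-cohort listing a supplement to those tables.

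For the by-stratum tables, prespecify one rule for assigning wrong-cohort participants to a stratum and apply it to both arms. Because the qIRV dose level may differ by stratum, either footnote the wrong-cohort qIRV recipients or add a sensitivity table that excludes wrong-cohort participants from both arms.

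The cost is about one sentence for the population, one for the stratum rule, and a check of the population flags. The downside is that a stratum table may include a few people given the other stratum's dose level; the listing identifies them.

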5. GENERAL METHODOLOGY AND CONVENTIONS

5.1. Hypotheses and Decision Rules

The hypotheses for the primary efficacy and secondary immunogenicity objectives are stated below.

5.1.1. Efficacy

The primary efficacy objective of the study is to evaluate the noninferiority and superiority of the VE of qIRV against first-episode LCI cases with associated per-protocol ILI (caused by any strain), with symptom onset from 14 days after vaccination, compared to QIV for each age group (participants 18 through 64 years of age and ≥ 65 years of age) independently.

The statistical hypothesis is defined below, and the evaluable efficacy population will be used for hypothesis testing.

$H_0: RVE \leq CCI$

CCI

$H_0: p \leq CCI$

The following hypothesis for superiority of VE of qIRV against first-episode LCI cases with associated per-protocol ILI (caused by any strain), with symptom onset from 14 days after vaccination, compared to QIV, will be tested for each age group.

$H_0: RVE \leq CCI$

The primary noninferiority efficacy objective for each age group will be achieved if the lower bound of the 95% CI of RVE is C_{lower} , and the superiority efficacy objective will be met if the lower bound of the 95% CI of RVE is $C_{superior}$.

5.1.2. Immunogenicity

A secondary immunogenicity objective of the study is to evaluate the noninferiority of the immune response to qIRV at 4 weeks after vaccination compared to QIV for each age stratum (participants 18 through 64 or ≥ 65 years of age). For antibody titers measured by HAI assays CCI , 2 statistical hypotheses for each targeted strain will be defined, as described below, and the evaluable immunogenicity population (HAI assays CCI) will be used for hypothesis testing in each age stratum:

H₀₁: CCI

where CCI corresponds to a CCI margin for noninferiority, and CCI, CCI, CCI, CCI from the qIRV group and the QIV group, respectively, measured 4 weeks after vaccination.

H₀₂: CCI

where CCI are the proportions of participants achieving seroconversion at 4 weeks after vaccination for the qIRV group and QIV group, respectively, measured 4 weeks after vaccination.

For antibody titers measured by HAI assays CCI 2 statistical hypotheses for each targeted strain will be defined as described above based on the evaluable immunogenicity population (HAI assays CCI).

5.1.3. Multiplicity Adjustment

There are 2 hypothesis tests for the primary efficacy objectives (noninferiority, superiority) in each group (18 through 64 years of age, ≥ 65 years of age).

There are 8 hypothesis tests for the secondary immunogenicity objectives CCI assays, separately, with 2 statistical hypotheses for each of the 4 targeted strains for each age stratum (participants 18 through 64 and ≥ 65 years of age).

Only immunogenicity data collected from the CCI will be used for the immunogenicity noninferiority objectives.

For both age strata (participants 18 through 64 and ≥ 65 years of age), the hypothesis for the primary noninferiority efficacy objective will be tested first, followed by the hypothesis for the primary superiority efficacy objective. The superiority efficacy objective will be tested only after the noninferiority efficacy objective has been achieved. The hypotheses related to the secondary immunogenicity objective (HAI assays CCI) for each age stratum will be tested after both primary efficacy objectives in the respective age stratum have been achieved. Within the set of hypotheses related to HAI assays CCI, the hypotheses testing will be performed in their associated strain, CCI. The hypotheses related to the secondary immunogenicity objective assessed using HAI assays CCI for each age stratum will be tested with same testing order CCI (CCI) after the secondary immunogenicity objective (HAI assays CCI) in the respective age stratum has been achieved.

CCI

A fixed-sequence testing procedure will be used to control the overall 1-sided type I error at CCI for all efficacy and immunogenicity hypotheses within each age stratum. The 1-sided alpha level of CCI will be used for each hypothesis that can be tested based on this strategy.

All vaccine efficacy estimations with any additional LCI cases collected after primary analysis will be descriptively summarized with a 95% CI. No type I error will be allocated to the remaining secondary endpoints or exploratory endpoints.

